6.5 Interim Efficacy Analysis Set

The Interim Efficacy Analysis Set is a subset of the safety analysis set. The Interim efficacy analysis set includes subjects whose data cut-off date is at least 9 weeks after the first dose date of tarlatamab or AMG 404. Subjects who stopped disease assessments prior to 9 weeks will be included in this analysis set if the data cutoff is at least 9 weeks after their first dose date.

7. Planned Analyses

7.1 Interim Analysis and Early Stopping Guidelines

Safety data will be reviewed on an ongoing basis.

During dose exploration (Part 1) and formally during dose level review meetings (DLRMs), Amgen, in consultation with the site investigators, will review all available cumulative data by cohort prior to making dose escalation or dose de-escalation recommendation. Adverse events and DLTs observed in all subjects will be evaluated continually and fully integrated into all DLRMs and considered in all enrolment and dosing decisions.

During dose expansion (Part 2), Amgen will conduct evaluations of the ongoing grade 4 or higher treatment-related TEAEs to assess if the threshold for possible early trial termination has been reached. The safety interim will occur for every subjects

Date: 27 Sep 2024 Page 30 of 51

enrolled who have had opportunity to have at least of follow up since the first dose of tarlatamab. If this threshold is met, enrollment to dose expansion will be halted pending review of safety data by the DLRT. After receiving the DLRT recommendation, Amgen will choose to take one of the following actions.

- Terminate the trial
- Amend the protocol to potentially improve the benefit/risk for subjects (eg, increase safety monitoring, modify dose/schedule, mandate premedication)
- Continue dose expansion without any changes.

The stopping rules use a Bayesian approach proposed by Thall (Thall et al, 1995) to terminate the study if the posterior probability that the grade 4 or higher treatment related TEAE rate is greater than 20% is > 80%. The stopping boundaries assume a prior distribution of Beta (0.40, 1.60) are presented in **Table 4** and the operating characteristics with pre-specified batch size of new subjects per batch are presented in **Table 5**.

Table 4. Stopping Boundary for Dose Expansion with Posterior Probability of 80% and Grade 4 or Higher Treatment-related Adverse Event Limit of 20%

Number of Subject	Stop Subjects if Observing This Many Grade 4 or Higher Treatment-related Adverse Events
	≥ 4
	≥ 6
	≥ 9
	Dose Expansion Complete

 Table 5. Operating Characteristics with Batch Size of
 Subjects

True Grade 4 or Higher	Probability of Early	Average Dose Expansion
Treatment-related	Stopping of Dose	Sample Size
Adverse Event Rate	Expansion	-
0.10	2.0%	39.5
0.15	9.7%	37.6
0.20	25.8%	33.9
0.25	47.7%	28.8
0.30	69.2%	23.4

8.1 General Principles

The objective of the data screening is to assess the quantity, quality, and statistical characteristics of the data relative to the requirements of the planned analyses.

8.2 Data Handling and Electronic Transfer of Data

The Amgen Global Study Operations-Data Management (GSO-DM) department will provide all data to be used in the planned analyses. This study will use the RAVE database. The database will be subject to edit checks outlined in the Clinical Data Management Plan (DMP). See details of this section in the DMP.

8.3 Handling of Missing and Incomplete Data

The following imputation for missing or incomplete data will be performed if required: Incomplete adverse event, concomitant medication, death and time to event dates missing data will be imputed as described in Appendix A.

8.4 Detection of Bias

Lack of protocol compliance and the potential for biased statistical analyses will be examined by assessing the incidence of important protocol deviations in each cohort. The clinical study team will identify and document the criteria for important protocol deviations.

8.5 Outliers

Pharmacokinetic (PK) concentration data will be evaluated for outliers by visual inspection, and decision to re-assay individual samples will be made in accordance with standard pharmacokinetic evaluation practice. Descriptive statistics will be used to identify potential outliers in key variables. Suspected outliers will be included in all analyses unless there is sufficient scientific justification to exclude them.

8.6 Distributional Characteristics

Where appropriate, the assumptions underlying the proposed statistical methodologies will be assessed. If required data transformations or alternative non-parametric methods of analyses will be utilized.

8.7 Validation of Statistical Analyses

Programs will be developed and maintained and output will be verified in accordance with current risk-based quality control procedures.

Date: 27 Sep 2024 Page 33 of 51

Tables, figures, and listings will be produced with validated standard macro programs where standard macros can produce the specified outputs.

The production environment for statistical analyses consists of Amgen-supported versions of statistical analysis software; for example, the SAS System version 9.4 or later.

9. Statistical Methods of Analysis

9.1 General Considerations

Descriptive statistics will be provided for selected demographics, safety, pharmacokinetic, efficacy data by dose, dose schedule, and time as appropriate. Descriptive statistics on continuous data will include means, medians, standard deviations and ranges, while categorical data will be summarized using frequency counts and percentages. Graphical summaries of the data may also be presented. Confidence intervals (CI) for proportions will be estimated using an exact method proposed by Clopper-Pearson (Clopper and Pearson, 1934). Kaplan-Meier methods will be used to estimate the median and percentiles for time to event endpoints with CI calculated using the Brookmeyer and Crowley (Brookmeyer and Crowley, 1982) method. Kaplan-Meier methods will be used to estimate landmarks for time to event endpoints (eg, 1-year OS) with the Greenwood formula (Kalbfleisch and Prentice, 1980) used to estimate the standard error used in CI calculation.

9.2 Subject Accountability

The number and percentage of subjects who were enrolled, received investigational product, discontinued from investigational product (including reasons for discontinuing, completed study), discontinued the study (including reason for discontinuing) will be summarized by dose/cohort, combining data from each part and overall. Key study dates for the first subject enrolled, last subject enrolled, and last subject's end of study will be presented.

A subject listing and summary noting inclusion in each analysis subset will be provided for all subjects enrolled. A subject listing noting duration of tarlatamab and AMG 404 administrations, reason for discontinuation of treatment, and reason for discontinuing the study will be provided.

Date: 27 Sep 2024 Page 34 of 51

9.3 Important Protocol Deviations

Important Protocol Deviations (IPDs) categories are defined by the study team before the first subject's initial visit and updated during the IPD reviews throughout the study prior to database lock. These definitions of IPD categories, subcategory codes, and descriptions will be used during the course of the study. Eligibility deviations are defined in the protocol. The final IPD list is used to produce the Summary of IPDs table and the List of Subjects with IPDs. In addition, a separate listing of all inclusion and exclusion deviations will be provided.

9.4 Demographic and Baseline Characteristics

The following descriptive summaries of demographic and baseline characteristics will be produced by dose/cohort, combining data from each part (i.e., Part 1 – Dose exploration phase and Part 2 – Dose expansion phase) and overall.

The Demographic characteristics will include – age at enrollment in years (summary statistics), age groups (<65, ≥65), sex (Male, Female), race (White, Asian, Black or African American, vs other categories depending on frequency observed) and ethnicity (Hispanic, Not Hispanic). If multiple races have been reported for a subject, the subject will be categorized as multiple.

The baseline characteristics will include – Height, Weight, Body Mass Index, sum of diameters of target lesions at baseline, presence of metastatic disease, Eastern Cooperative Oncology Group (ECOG) performance status (0, 1), Time from initial diagnosis to enrollment, Disease stage at initial diagnosis (Limited, Extensive), Prior lines of therapy (1, 2, 3, >3), Prior anti-cancer therapy (Yes, No), Prior radiotherapy for current malignancy (Yes, No), prior PD-1 or PD-L1, platinum sensitivity to first line platinum based treatment, Prior surgery for current malignancy (Yes, No), neurological exams, writing test and mini-mental status exams, Brain metastases at initial diagnosis (No brain mets present, Brain mets present – treated, Brain mets present – not treated), Liver metastases at initial diagnosis (No liver mets present, Liver mets present), Smoking history (Never, Current, Former), ECHO or MUGA scan, if available.

A listing of the demographic and baseline characteristics will be provided if required. In additional listings of medical and surgical history, prior anti-cancer therapy and prior radiation therapy usage will be provided, if required.

Date: 27 Sep 2024 Page 35 of 51

9.5 Efficacy Analyses

Table 7. Efficacy Endpoint Summary Table

Endpoint	Primary Summary and Analysis method	Interim Analysis Set	Primary Analysis and Final Analysis Set
ORR	The percentage of subjects with an	Interim Efficacy	Safety Analysis
	objective response (per modified	Analysis Set	Set
	RECIST criteria v1.1) will be		
	summarized by planned dose level		
	along with exact 2-sided 95%		
	confidence interval using Clopper–		
	Pearson method.		
	Subjects without a post-baseline		
	tumor assessment will be		
	considered non-responders.		
DCR	The percentage of subjects with	Interim Efficacy	Safety Analysis
	disease control (per modified	Analysis Set	Set
	RECIST criteria v1.1) will be		
	summarized along with 95% exact		
	2-sided confidence interval using		
	Clopper –Pearson method.		
	Subjects without a post-baseline		
	tumor assessment will be		
	considered non-responders.		
DOR	The K-M quartiles along with 2-	Interim Efficacy	Safety Analysis
	sided 95% CIs and rates for	Analysis Set	Set
	selected duration of response (eg,		
	>3, >6, >9, >12 months) will be		
	estimated by planned dose level		
	using Kaplan-Meier method		
TTR	Time to response (TTR) will be	N/A	Safety Analysis
	summarized with the non-missing		Set
	sample size (n), mean, standard		
	deviation, median, Q1, Q3,		
	minimum, and maximum for		

Date: 27 Sep 2024 Page 36 of 51

Endpoint	Primary Summary and Analysis method	Interim Analysis Set	Primary Analysis and Final Analysis Set
	subjects who achieve best overall response of CR, or PR.		
PFS	KM curve for PFS, K-M quartiles along with 2-sided 95% CIs and rate for selected time points (eg, 6-months PFS, 1 year [12 months] PFS) will be estimated by planned dose level using Kaplan-Meier method.	Interim Efficacy Analysis Set	Safety Analysis Set
OS	KM curve for OS, K-M quartiles along with 2-sided 95% CIs and rate for selected time points (eg, 6-months PFS, 1 year [12 months] PFS) will be estimated by planned dose level using Kaplan-Meier method.	Interim Efficacy Analysis Set	Safety Analysis Set

The efficacy endpoints include ORR, DCR, DOR, TTR, PFS, and OS. For primary and final analyses, the analysis of efficacy endpoints will be done on the Safety Analysis Set. For interim analysis, the analysis of efficacy endpoints will be done on the Interim Efficacy Analysis Set. Overall response assessments occurring after the start of the first subsequent anticancer therapy will not be included in the efficacy analyses.

9.5.1 Analyses of Primary Efficacy Endpoint(s)/Estimand(s)

Not applicable for this study.

9.5.2 Analyses of Secondary Efficacy Endpoint(s)

The objective response rate and disease control rate (per modified RECIST criteria v1.1) will be summarized by cohort along with 95% exact 2-sided confidence interval using Clopper-Pearson method (Clopper and Pearson, 1934). The subjects without a post-baseline tumor assessment will be considered non-responders.

The duration of response (DOR) will be summarized only for those subjects who achieve a best overall response (either PR or CR). The distribution of DOR including median and quartiles will be presented by cohort using Kaplan-Meier (KM) method

Date: 27 Sep 2024 Page 37 of 51

along with 2-sided 95% CI using Brookmeyer and Crowley (Brookmeyer and Crowley, 1982) method. The KM rates of selected durations (eg, >3, >6, >9, >12 months) will also be reported. KM curve can be produced for DOR, provided at least of subjects achieve either CR or PR.

The distribution of PFS including median and quartiles will be presented by cohort using Kaplan-Meier method along with 2-sided 95% CI using Brookmeyer and Crowley (Brookmeyer and Crowley, 1982) method. The standard error used in CI calculation will be estimated using the Greenwood formula (Kalbfleisch and Prentice, 1980). The KM rates of selected time points (eg, 6-month PFS, 1-year PFS) will also be reported.

The overall survival (OS) will be analyzed using the same approach as described for the PFS endpoints.

9.5.3 Analyses of Exploratory Efficacy Endpoint(s)

Not applicable.

9.6 Safety Analyses

9.6.1 Analyses of Dose Limiting Toxicities

The subject incidence of DLT will be tabulated by planned dose level. The analysis of DLTs will be conducted on DLT analysis set. The subject incidence of DLTs will be used to estimate final DLT rates for each dose level using isotonic regression (Ji et al, 2010). Refer the Section 3.3 of adaptive design for more details.

9.6.2 Adverse Events

The **most recent version of** Medical Dictionary for Regulatory Activities (MedDRA) will be used to code all events categorized as adverse events to a system organ class and a preferred term. AEs of interest (EOI) categories will be based on search strategies defined by Medical Coding.

The subject incidence of adverse events will be summarized for all treatment-emergent adverse events, treatment-related adverse events, serious adverse events, grade 3 and above, grade 4 and above and fatal adverse events, adverse events leading to discontinuation of investigational product, adverse events leading to interruption and/or reduction of investigational product.

Date: 27 Sep 2024 Page 38 of 51

Subject incidence of all treatment-emergent adverse events, treatment-related treatment-emergent adverse events, serious treatment-emergent adverse events, grade 3 or above treatment-emergent adverse events, fatal treatment-emergent adverse events, treatment-emergent/treatment-related adverse events leading to interruption and/or reduction of investigational product, and treatment-emergent/treatment-related adverse events leading to discontinuation of investigational product or other protocol-required therapies will be tabulated for each cohort by preferred term or by system organ class and preferred term in descending order of frequency of highest dose group. The tables will also be presented by worse grade, wherever appropriate or applicable.

The summary of the subject incidence of treatment-emergent adverse events, treatment-related adverse events, serious adverse events and fatal adverse events for the extended period will also be provided.

The severity of each adverse event will be graded using CTCAE 4.0 criteria and CRS events will be graded using Lee et al, 2014 criteria.

Adverse Events of Interest (EOI):

EOIs identified for tarlatamab:

Cytokine Release Syndrome (Broad), Cytokine Release Syndrome (Narrow), Neutropenia (Broad), Neutropenia (Narrow), Immune effector Cell Associated Neurotoxicity Syndrome (ICANS) and associated neurological events (Broad), Neurological Events [Nervous system disorders (SOC) + Psychiatric disorders (SOC)], and Hypersensitivity events [Hypersensitivity (SMQ Broad)/Anaphylactic reactions (SMQ Narrow)].

For the list of EOIs mentioned above, the subject incidence of treatment-emergent adverse events of interest (standardized MedDRA queries and/or Amgen Medical Queries), grade ≥ 2 , grade ≥ 3 , grade ≥ 4 , serious, fatal, and events leading to interruption, reduction or discontinuation of IP will be summarized.

The subject incidence of above treatment-emergent EOIs will be tabulated by preferred term. CRS will be graded according to Lee et al, 2014.

The summaries of time to onset of EOI from first dose of IP (days), which comes earlier, time to onset of EOI after each dose from last prior dose of IP (days), which comes later(days), time to onset of CRS from first dose of tarlatamab (hours), time to onset of CRS from each last prior tarlatamab dose (hours), and duration of treatment-emergent

Date: 27 Sep 2024 Page 39 of 51

EOI will be provided. Additionally, summaries of time to onset and duration of EOI will be provided for grade 2 or higher and grade 3 or higher EOIs respectively.

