Tumor lysis syndrome, a severe, life-threatening disorder that can occur in highly proliferative malignancies or with debulking of extensive tumor burden, is characterized by a group of metabolic disorders caused by the massive and abrupt release of cellular metabolites into the blood after lysis of the malignant cells (Coiffier et al, 2008). The metabolic complications predispose patients with cancer to various clinical complications, including renal failure, seizures, cardiac arrhythmias, and even sudden death. Tumor lysis syndrome occurs primarily during treatment of neoplasms which are rapidly proliferating such as aggressive lymphomas and acute leukemias. It has been reported to occur rarely in solid tumors. With the introduction of more effective therapeutic agents, the possible occurrence of TLS in patients with bulky, treatment-sensitive solid tumors must be recognized. Therefore, there is a risk of TLS in humans with administration of tarlatamab.

2.3.3.2 AMG 404

AMG 404 has been evaluated as a monotherapy agent in a FIH, phase 1 study (Study 20180143) of subjects with advanced or metastatic solid tumors. Based on the

Protocol Number: 20200439

Date: 05 June 2024 Page 37 of 176

available clinical data with AMG 404, hypothyroidism, colitis, and myasthenia gravis are identified risks of AMG 404. (Table 2-2).

Table 2-2. Key Safety Risks of AMG 404

Safety Risk	Description
Hypothyroidism	Administration of AMG 404 has been associated with hypothyroidism or blood thyroid stimulating hormone increased. Signs and symptoms that may be associated with hypothyroidism include fatigue, increased sensitivity to cold, constipation, dry skin, weight gain, hoarseness, muscle weakness, myalgia, arthralgia, menstrual disturbance, alopecia, bradycardia, hypercholesterolemia, depression, impaired memory, and enlarged thyroid gland (goiter).
	Hypothyroidism or blood thyroid stimulating hormone increased reported events did not lead to AMG 404 discontinuation or AMG 404 treatment interruption. Subjects should be monitored for laboratory values of thyroid stimulating hormone and Free T4, and signs and symptoms of hypothyroidism during AMG 404 treatment. Subjects should continue to be monitored after discontinuation of AMG 404 due to the risk of late onset hypothyroidism. Requirements for monitoring and management of hypothyroidism are provided in the clinical study protocol.

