2.3.3.3 Key Risks for Tarlatamab in Combination with AMG 404

To date, there is limited safety data with BiTE® molecules in combination with PD-1 inhibitors. However, in a phase 1 study, the combination of the BiTE® molecule blinatumomab with the PD-1 inhibitor nivolumab was reported to be safe and tolerable in a small number of subjects with ALL (Webster et al, 2018). No clinical or preclinical safety information is available for the combination of tarlatamab with AMG 404. In the ongoing tarlatamab FIH study (20160323), a

being conducted (tarlatamab dose level of mg in deemed safe and tolerable). Based on biological mechanism of action and initial clinical safety information from the monotherapy study with tarlatamab (20160323), the key safety information and additional risks described for monotherapy would also be expected along with the key risks described for AMG 404. Moreover, with

Protocol Number: 20200439

Date: 05 June 2024 Page 39 of 176

combination treatment, adverse events may be more severe and occur at different time points and/or dose levels in comparison to monotherapy. In particular, synergistic activation of T cells is expected and may contribute to more severe immune-related toxicities. Pneumonitis is an immune mediated toxicity for the PD-1 inhibitor class of drugs and has been observed in tarlatamab. Refer to Section 6.8 for specific recommendations regarding the mitigation and management of CRS and infusion-related reactions. Key safety risks for the combination of tarlatamab and AMG 404 include:

- exacerbated CRS and/or infusion reactions
- exacerbated pituitary dysfunction
- exacerbated neurologic events

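### The SAP's events of interest are defined for tarlatamab only, so immune-related events and pituitary dysfunction get no grouped summary for the combination

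*SAP*

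**What the plan says.** SAP 9.6.2 defines a single set of adverse events of interest, under the heading "EOIs identified for tarlatamab". The set holds cytokine release syndrome (broad and narrow), neutropenia (broad and narrow), ICANS with associated neurological events, neurological events taken as two whole system organ classes, and hypersensitivity with anaphylactic reactions. Grouped summaries by grade, seriousness, fatality and effect on dosing are confined to that set: "For the list of EOIs mentioned above, the subject incidence of treatment-emergent adverse events of interest". Summaries of time to onset and duration are likewise given for events of interest. There is no corresponding list for AMG 404 or for the combination, although SAP Section 5 defines the investigational product as both agents.

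The protocol describes the combination's risks more widely. Section 2.3.3.3 says that "synergistic activation of T cells is expected and may contribute to more severe immune-related toxicities". Its list of key risks has three entries: cytokine release syndrome and/or infusion reactions, "exacerbated pituitary dysfunction", and neurologic events. It also notes pneumonitis as a PD-1 class toxicity already seen with tarlatamab. Section 2.3.3.2 states that "hypothyroidism, colitis, and myasthenia gravis are identified risks of AMG 404".

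**The concern.** The study exists to describe the safety of giving the two agents together, and Protocol 2.3.3.3 says that no clinical or preclinical safety information was available for this pair. The event-of-interest list decides which toxicities are reported as a clinical entity and which are left spread over preferred terms. Two of the entities that the protocol itself raises for the combination are outside the list. Immune-related toxicity is the more exposed. Protocol 6.2.2.2.1 says it can affect several body systems at once, and the organ rows of Table 6-2 run from lung, bowel and liver to the endocrine organs, kidney, skin, brain and heart. Individual terms may each look rare in a small study while the category is not. At stake is whether the report states the combination's rate, severity, onset and duration for these categories, or leaves readers to assemble them after the fact.

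**Working it through.** **Plan's own figure.** The event-of-interest section gives no number, so the nearest is Protocol 9.2: with 10 (20) expansion subjects, the chance of seeing at least one event of 10% incidence is 65% (88%). 1 − 0.9^10 = 65.1% and 1 − 0.9^20 = 87.8%. Both reproduce.

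**Coverage.** The protocol's risks set against the SAP 9.6.2 list:

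| Risk | Source | Grouped in SAP 9.6.2? |
|---|---|---|
| Cytokine release syndrome | Protocol 2.3.3.3 | Yes, broad and narrow |
| Neurologic events | Protocol 2.3.3.3 | Yes, ICANS group and two organ classes |
| Infusion reactions | Protocol 2.3.3.3 | Not separately; possibly in part through the broad cytokine-release and hypersensitivity searches |
| Pituitary dysfunction | Protocol 2.3.3.3 | No |
| Immune-related toxicity, including pneumonitis | Protocol 2.3.3.3 (text, not its list) | No |
| Hypothyroidism, colitis, myasthenia gravis | Protocol 2.3.3.2 | None named; myasthenia gravis may fall in the neurologic group, depending on coding that the documents do not give |

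**Do other tables pool them?** SAP 9.6.2 tabulates adverse events by preferred term or by system organ class and preferred term. The class level is optional. Where used, it gives a subtotal within one class, which cannot count subjects once across lung, bowel, liver, endocrine and skin. Protocol 9.4.2.3.2 promises a table of significant treatment-emergent events but does not define significant. Medical Coding supplies search strategies for the categories that exist; nothing says that it adds categories.

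**Illustration of size.** Assumptions, not document figures: a category with true incidence P, split evenly over k preferred terms with no subject in two terms. For one row, p = P/k, and the chance of at least two subjects is 1 − (1 − p)^n − n·p·(1 − p)^(n − 1). For n = 20, P = 20%, grouped: 1 − 0.8^20 − 20 × 0.2 × 0.8^19 = 1 − 0.0115 − 0.0576 = 93.1%. The rest follow in the same way:

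| n | P | Grouped | Given row, 2 terms | 3 terms | 5 terms |
|---|---|---|---|---|---|
| 10 | 20% | 62.4% | 26.4% | 14.0% | 5.8% |
| 20 | 20% | 93.1% | 60.8% | 38.9% | 19.0% |
| 20 | 10% | 60.8% | 26.4% | 14.2% | 6.0% |
| 40 | 20% | 99.9% | 92.0% | 75.6% | 47.9% |

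The sizes 10 and 20 are those used in Protocol 9.2; 40 is an assumed larger size, close to the highest average expansion size in Protocol Table 9-3 (39.5).

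As a reported result, four affected subjects of 20 read as 20% (Clopper-Pearson 95% interval 5.7% to 43.7%) when grouped. If each has a different term, they read as four rows of 5% (0.1% to 24.9%). That full scatter is an extreme: with five equally likely terms, four subjects all differ with probability 1 × 4/5 × 3/5 × 2/5 = 19.2%. With fewer terms it is less likely, and with more terms it is more likely.

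**The case against.** The other side has several good points.

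- A reader might infer that none of the combination's key risks is pooled. That is not so. Of the three entries in Protocol 2.3.3.3, cytokine release syndrome and neurologic events have groups. Infusion reactions share an entry with cytokine release syndrome, and Protocol 6.8.1 says the two may be clinically indistinguishable. Only pituitary dysfunction has no group at all.
- A reader might infer that immune-related events can surface only as isolated preferred terms. The SAP also allows organ-class tables, and it tabulates events leading to interruption, reduction or discontinuation of either agent. Toxicities that require permanent discontinuation of AMG 404 under Table 6-2 count as dose-limiting (Protocol 6.2.1.4). Potential Hy's law cases are listed, and ACTH, cortisol, TSH and free T4 are collected.
- A reader might infer that the missing groups are what stop the analysis from showing whether AMG 404 raised toxicity. Under Protocol 6.4.1 all eligible subjects are assigned to both agents, and no hypothesis is tested. A grouped row would not answer that question either.
- The choice of events of interest is partly the sponsor's judgement. The SAP's change history shows that the list was revised, and the definitive output list sits in the Program Index, which is not among the documents. No escalation or stopping rule uses the list.

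All of this limits the point but does not remove it. Dose-limiting toxicities cover only the Part 1 observation window, whereas Protocol 6.2.2.2.1 says immune-related toxicity can appear months after the last dose. Organ-class totals still do not cross classes. Reliance on a Program Index or on later regrouping would leave the categories without definition in the SAP.

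**Conclusion.** The point holds as a gap in description. Immune-related events and pituitary dysfunction have no grouped summary, and infusion-related reactions have none of their own beyond possible partial capture. The combination's rate, grade, onset and duration for these categories is therefore not reported as a group, although combination safety is the primary objective. This part rests on the text alone and needs no assumption.

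The size does rest on assumptions: the category rate, the even split and the sample size. Within the range shown for 20 subjects, the chance of seeing two or more cases falls from 61–93% in a grouped row to 14–39% in any given one of three term-level rows. How much of the infusion-reaction risk is already captured cannot be settled, because the search terms are not in the documents. The change is worth making, but neither the dose decisions nor the Part 2 stopping rule depends on it.

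**What to change.** Before database lock, extend SAP 9.6.2 with event-of-interest groups for:

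1. Immune-related events, overall and by the organ categories of Protocol Table 6-2, including pneumonitis, with search terms set by Medical Coding.
2. Pituitary dysfunction. Hypophysitis will belong to both this group and group 1, so state that a subject counts once within each.
3. Infusion-related reactions, if Medical Coding finds that the broad cytokine-release and hypersensitivity searches do not capture them.

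Give each group the summaries already planned for the tarlatamab list: any grade, grade 2, 3 and 4 or higher, serious, fatal, leading to interruption, reduction or discontinuation, time to onset, and duration.

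The cost is a term list and a few more tables; no new data are required for term-based groups. The main weakness is specificity. The adverse event attributes in Protocol Section 11.4 include relatedness but no immune-mediated flag, and Table 6-2 is a management table rather than a search strategy. Groups built from terms such as rash, diarrhoea or raised transaminases will include some non-immune events. Showing treatment-related events beside all events would let the reader judge this.
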